3.2 DISCUSSION OF TRIAL DESIGN, INCLUDING THE CHOICE OF CONTROL GROUP(S)

The placebo control is required to control for investigator bias and/or beneficial effects of being in a clinical trial. The 2:1 randomization (active: placebo) is warranted in order to maximize the number of patients receiving active treatment and is being controlled for from a statistical standpoint. The rationale for switching responding patients to follow-up with no-treatment at Week 16 is to evaluate the duration of clinical response off treatment. In addition, patients who have not attained at least a 75% reduction in EASI score compared to baseline will have the opportunity to receive (or continue) active treatment.

3.3 SELECTION OF TRIAL POPULATION

3.3.1 Main diagnosis for trial entry

This study will include adult patients diagnosed with atopic dermatitis for at least 1 year who developed moderate to severe atopic dermatitis with documented inadequate response to topical corticosteroid and be willing to discontinue topical corticosteroid 7 days or systemic corticosteroid 4 weeks before first administration of trial treatment.

Please refer to Section [8.3.1](#) (Source Documents) for the documentation requirements pertaining to the in- and exclusion criteria.

3.3.2 Inclusion criteria

1. Signed and dated written informed consent in accordance with Good Clinical Practice (GCP) and local legislation prior to the start of any screening procedures
2. Male or female patients, 18 to 75 years of age at screening
3. Diagnosis of atopic dermatitis for at least 1 year
4. Moderate to severe atopic dermatitis defined as:
 - At least 10% Body Surface Area (BSA) of atopic dermatitis involvement at screening and baseline
 - Eczema Area and Severity Index (EASI) of at least 12 at screening and at least 16 at baseline
 - Investigator Global Assessment (IGA) of at least 3 at screening and baseline
5. Documented history of inadequate response to topical corticosteroid as judged by the investigator
6. Willing to use a standard emollient for the duration of the study
7. Women of childbearing potential (WOCBP)² must be ready and able to use highly effective methods of birth control per ICH M3 (R2) that result in a low failure rate of less

² A woman is considered of childbearing potential (WOCBP), i.e. fertile, following menarche and until becoming post-menopausal unless permanently sterile.

Permanent sterilisation methods include hysterectomy, bilateral salpingectomy and bilateral oophorectomy. Tubal ligation is NOT a method of permanent sterilisation.

than 1% per year when used consistently and correctly. A list of contraception methods meeting these criteria is provided in the patient information.

3.3.3 Exclusion criteria

1. Use of topical corticosteroids or other agents for atopic dermatitis within 7 days prior to first dose of trial treatment.
2. Use of systemic corticosteroids or other agents for atopic dermatitis within 4 weeks prior to first dose of trial treatment (for more details refer to Table [4.2.3.1: 1](#)).
3. Women who are pregnant, nursing, or who plan to become pregnant while in the trial. Women who stop nursing before the study drug administration do not need to be excluded from participating; they should refrain from breastfeeding up to 16 weeks after the last study drug administration (see [Section 4.2.3.3](#))
4. Patient with a transplanted organ (with exception of a corneal transplant > 12 weeks prior to screening) or who have ever received stem cell therapy (e.g., Prochymal).
5. Any documented active or suspected malignancy or history of malignancy within 5 years prior to the screening visit, except appropriately treated basal cell carcinoma of the skin, squamous cell carcinoma of the skin or in situ carcinoma of uterine cervix.
6. Use of any restricted medication as specified in Table [4.2.3.1: 1](#) or any drug considered likely to interfere with the safe conduct of the study, as assessed by the investigator.
7. History of allergy/hypersensitivity to the systemically administered trial medication agent or its excipients.
8. Active systemic infections (Fungal and bacterial disease) during the last 2 weeks prior to first drug administration, per investigator assessment.
9. Relevant chronic or acute infections (exception: common cold) including human immunodeficiency virus (HIV) or viral hepatitis. A patient can be re-screened if the patient was treated and is cured from the acute infection.
10. Active or Latent TB:

Patients with active tuberculosis are excluded.

Patients with a positive QuantiFERON TB test during screening are excluded, unless:

- Patient had previous diagnosis of active or latent TB and has completed appropriate treatment per local practice/guidelines within the last 3 years and at least 6 months before first administration of trial medication under this protocol (patients may be re-screened once to meet this criterion)
- Patients with suspected false positive or indeterminate QuantiFERON TB result may be re-tested once
- If the QuantiFERON TB test result is not available or provides indeterminate results after repeat testing: A tuberculin skin test reaction $\geq 10\text{mm}$ ($\geq 5\text{mm}$ if receiving $\geq 15\text{mg/d}$ prednisone or its equivalent) is considered positive.

Proprietary confidential information © 2020 Boehringer Ingelheim International GmbH or one or more of its affiliated companies

11. Currently enrolled in another investigational device or drug trial, or less than 30 days or 5 half lives, whichever is longer since ending another investigational device or drug trial(s), or receiving other investigational treatment(s).
12. Evidence of a current or previous disease, medical condition (including chronic alcohol or drug abuse or any condition) other than AD, surgical procedure, psychiatric or social problems, medical examination finding (including vital signs and ECG), or laboratory value at the screening outside the reference range that in the opinion of the investigator is clinically significant and would make the study participant unreliable to adhere to the protocol, comply with all study visits/procedures or to complete the trial compromise the safety of the patient or compromise the quality of the data.
13. Major surgery (major according to the investigator) performed within 12 weeks prior to first study drug administration or planned during the study (e.g. hip replacement, aneurysm removal, stomach ligation).
14. Severe, progressive, or uncontrolled hepatic disease, defined as >3-fold Upper Limit of Normal (ULN) elevation in AST or ALT or alkaline phosphatase, or >2-fold ULN elevation in total bilirubin.

3.3.4 Withdrawal of patients from treatment or assessments

Patients may discontinue trial treatment or withdraw consent to trial participation as a whole (“withdrawal of consent”) with very different implications; please see [Sections 3.3.4.1](#) and [3.3.4.2](#) below.

Every effort should be made to keep the patients in the trial: if possible on treatment, or at least to collect important trial data.

Measures to control the withdrawal rate include careful patient selection, appropriate explanation of the trial requirements and procedures prior to trial enrolment, as well as the explanation of the consequences of withdrawal.

The decision to discontinue trial treatment or withdraw consent to trial participation and the reason must be documented in the patient files and Electronic Case Report Form (eCRF). If the reason for discontinuation is death, this should be reported on the SAE form as well, regardless of causal relationship.

3.3.4.1 Discontinuation of trial treatment

An individual patient will discontinue trial treatment if:

- The patient wants to discontinue trial treatment, without the need to justify the decision.
- The patient has repeatedly shown to be non-compliant with important trial procedures and, in the opinion of both, the investigator and sponsor representative, is not willing or able to adhere to the trial requirements in the future.
- The patient needs to take concomitant medication that interferes with the investigational medicinal product or other trial treatment, please see Section [4.2.3](#).
- The patient can no longer receive trial treatment for medical reasons (such as surgery, adverse events, other diseases, or pregnancy).

- For individual stopping rules related to specific adverse events, please see Section [4.2](#).

In case of a temporary discontinuation of trial treatment, trial treatment should be restarted as soon as medically justified, please see Section [4.1.4](#), [4.2.2](#). Even if the trial treatment is discontinued, the patient remains in the trial and, given his/her agreement, will undergo the procedures for early treatment discontinuation and follow up as outlined in the [Flow Chart](#) and Section [6.2.3](#).

3.3.4.2 Withdrawal of consent to trial participation

Patients may withdraw their consent to trial participation at any time without the need to justify the decision.

If a patient wants to withdraw consent, the investigator should be involved in the discussion with the patient and explain the difference between trial treatment discontinuation and withdrawal of consent to trial participation, as well as explain the options for continued follow up after trial treatment discontinuation, please see Section [3.3.4.1](#) above.

3.3.4.3 Discontinuation of the trial by the sponsor

Boehringer Ingelheim (BI) reserves the right to discontinue the trial overall or at a particular trial site at any time for the following reasons:

1. Failure to meet expected enrolment goals overall or at a particular trial site.
2. Emergence of any efficacy/safety information invalidating the earlier positive benefit-risk-assessment that could significantly affect the continuation of the trial.
3. Violation of GCP, the trial protocol, or the contract impairing the appropriate conduct of the trial.

The investigator / the trial site will be reimbursed for reasonable expenses incurred in case of trial termination (except in case of the third reason).

4. TREATMENTS

4.1 INVESTIGATIONAL TREATMENTS

The investigational product has been manufactured by BI Pharma GmbH & Co. KG, Biberach, Germany. The BI 655130 molecule is an anti-human IL36 receptor monoclonal antibody heterodimer with a molecular weight of approximately 146 kDa.

BI 655130 solution for infusion (i.v. administration) is formulated at 60 mg/mL presented in a 10 mL vial with a nominal fill volume of 7.5 mL (450 mg).

4.1.1 Identity of the Investigational Medicinal Products

Table 4.1.1: 1 Study Compound

Substance:	BI 655130
Pharmaceutical formulation:	Solution for infusion
Source:	BI Pharma GmbH & Co. KG, Biberach, Germany
Unit strength:	BI 655130 450 mg/vial (60 mg/mL), 7.5 mL fill volume
Posology:	600 mg i.v. infusion once every 4 weeks
Method and route of administration:	i.v. infusion

Table 4.1.1: 2 Placebo comparator

Substance:	Placebo
Pharmaceutical formulation:	Solution for infusion
Source:	BI Pharma GmbH & Co. KG, Biberach, Germany
Unit strength:	Placebo to BI 655130 450 mg/vial (60 mg/mL), 7.5 mL fill volume
Posology:	0 mg i.v. infusion once every 4 weeks
Method and route of administration:	i.v. infusion

At the time of use the i.v. solutions for dosing will be prepared as detailed in the instruction in the ISF.

4.1.2 Selection of doses in the trial and dose modifications

A fixed rather than weight-based dose regimen of single dose of 600 mg has been selected. Early trials of therapeutic monoclonal antibodies often investigate body-weight-based regimens to reduce the inter-subject variability in drug exposure. However, there is generally only a modest contribution of body weight to the overall pharmacokinetic (PK) and pharmacodynamic (PD) variability of monoclonal antibodies. Furthermore, monoclonal antibodies are highly target specific and offer a relatively large therapeutic window compared to new chemical entities. Therefore, most monoclonal antibodies are approved at fixed doses in antibody/target excess in order to cover target turnover and maximize efficacy [[R10-6267](#); [R13-4749](#); [R13-4753](#); [R13-4750](#); [R13-4754](#)].

4.1.3 Method of assigning patients to treatment groups

An Interactive Response Technology (IRT) will be used to screen and randomise eligible patients, perform subsequent drug assignment, manage initial/re-supply ordering of drug supplies and handle emergency un-blinding. The investigator will receive all necessary instructions to access IRT from the Sponsor or chosen provider. Detailed IRT functions and procedures will be documented in the user requirement specifications mutually agreed to by the sponsor and the IRT vendor. Patients will be randomly assigned to one of the treatment groups through the assignment of medication which will be treatment group-specific (Section [3.1](#)). For technical and statistical features of the treatment allocation process, please see Sections [4.1.4](#) and [7.6](#).

During Visit 2 (W0) and after the patient's eligibility has been confirmed, the treatment will be assigned via IRT. Patients will be randomized to receive BI 655130 600 mg or placebo in a ratio of 2:1. The assignment will occur in a blinded fashion via IRT.

During Visit 7 (W16) patients will be evaluated with the EASI scoring system (see Section [5.1](#)) and based on the response will be reassigned via IRT to receive BI 655130 600 mg or no treatment at all. The re-assignment will occur in an open label fashion.

4.1.4 Drug assignment and administration of doses for each patient

In all patients, the infusion solution is intended to be intravenously administered over a period of 90 minutes. In case of safety concerns, e.g. due to infusion reactions, it is at the discretion of the investigator or his/her designee to adapt the infusion scheme, including but not limited to slowing down the infusion rate, stopping the infusion, and provided no further safety concern exists, restarting at a slower rate. Regardless, the total duration of infusion should not exceed 180 minutes (3 hours). Further based on his/her medical judgment the investigator will provide medications as needed.

The administration of the trial medication will be done under the supervision of the investigating physician or a designee. The so-called four-eye principle (two-person rule) should be applied for administration of trial medication and – if applicable – its preparation, if correct dosage cannot be ensured otherwise.

Prior to each administration of study drug, a urine pregnancy test will be performed on site. If this test has a positive result, the administration of study drug should not proceed and this urine test should be confirmed by a serum pregnancy test.

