4.2 OTHER TREATMENTS, EMERGENCY PROCEDURES, RESTRICTIONS

4.2.1 Other treatments and emergency procedures

Stable doses of concomitant therapies for chronic conditions, for which neither the condition nor the treatment are judged to exclude the patient from participation (see Section [3.3](#)), are permissible. All concomitant medications should be carefully evaluated by the investigator and the Clinical Trial Manager should be contacted when there are questions regarding concomitant medications.

Proprietary confidential information © 2020 Boehringer Ingelheim International GmbH or one or more of its affiliated companies

During the trial, if the severity and progression of the disease worsens, the investigator can treat the patient with Standard of Care (SoC) of his/her choice. All efforts should be made to inform the patient of the importance of coming to the protocol specified visits (See [Flow Chart](#)) up to the EoS visit. Patients refusing to return to the study site for scheduled visits after the end of treatment should at least provide safety information by phone at the respective visits.

Overall, the choice of the escape treatment i.e Standard of Care treatment will be left at the discretion of the investigator. The sponsor will not provide/supply SoC treatment(s) to the sites. If a patient receives escape treatment the decision to maintain the patient on trial treatment will be decided with discussion between the investigator and sponsor.

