4.2.2 Emergency procedures

Infusion reactions including anaphylactic reaction

In case of infusion reactions including anaphylactic reaction emerging during or after infusion of trial medication, the investigator should consider in accordance with severity of the reaction and local standard of care to:

- Immediately interrupt the infusion
- Treat with systemic anti-histamines, i.v. steroids, and in case of a severe allergic reaction (eg, anaphylactic reaction) epinephrine

Also draw a plasma sample for IgE and ADA as detailed in the Lab Manual (Central laboratory). Consider also the evaluation of histamine, serum tryptase, and complement components.

In case of infusion reaction, based on patient's clinical course and medical judgment, the infusion may be re-initiated in case of mild or moderate infusion reactions (according to Rheumatology Common Toxicity Criteria (RCTC) V2) at lower speed with gradual increase to complete the infusion as detailed in the Instructions for Preparation and Handling of BI 655130 in the ISF. In any case, the total duration of infusion should not exceed 180 minutes (3 hours).

In case of potential systemic allergic reaction, blood samples for determination of serum tryptase will be collected 0.5 h, 2 h, 6 h, 24 h after onset of the event.

In case of suspected drug related anaphylactic reaction (Appendix [10.1.1](#)) the investigator should discontinue treatment permanently with BI 655130.

Severe infections (according to RCTC V2), serious infections, opportunistic or mycobacterium tuberculosis infections.

Treatment of the infection should be initiated promptly according to local standard of care. No further trial medication should be administered until the active infection has resolved. Treatment with BI 655130 may be restarted when the patient has recovered according to investigator's assessment.

Overall, the choice of Standard of Care treatment will be left at the discretion of the investigator. The sponsor will not provide/supply SoC treatment (s) to the sites.

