5.2.4 ECG

ECG measurements will always precede blood sampling to avoid impact of sampling on the ECG results. The 12-lead ECGs will be recorded and reviewed prior to dosing as scheduled in the [Flow Chart](#). The investigator or a designee will evaluate whether the ECG is normal or abnormal and whether it is clinically relevant, if abnormal. ECGs may be repeated for quality reasons and the repeated recording used for analysis. No central laboratory will be used for ECG recording.

Additional ECGs may be recorded for safety reasons. The electronic version, if applicable, or dated and signed printouts of the ECG, will be regarded as source data and will be stored in the patient's medical file.

Clinically relevant abnormal findings will be reported either as baseline condition (if identified at the screening visit) or as adverse events and will be followed up and/or treated as medically appropriate.

Other Safety Parameters:

In case of an infusion reaction, monitor the patient per standard of care, grade the intensity of the reaction according to RCTC V2 grading (cf. ISF) and proceed as described in Section [4.2.1](#).

All cases of malignancies that are detected during the trial will be reported as SAEs.

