6.2.2.1 Clinical monitoring after study drug administration

During i.v. drug administration, vital signs will be assessed pre-dose, at approximately 5 minutes after the end of infusion, and 60 minutes after the end of infusion. Patients should be closely monitored for signs and symptoms of hypersensitivity reactions for approximately 1

hour after the end of infusion. Hypersensitivity reactions should be treated according to medical standards (See Section [4.2.2](#)).

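### Protocol 4.1.4 and 4.2.2 state the condition for restarting an infusion after a reaction differently and neither is said to govern; 5.2.4 points to a section without the procedure

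*Protocol*

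**What the plan says.** Four sections of the protocol bear on restarting an infusion after a reaction.

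- **4.1.4 (drug assignment and administration).** When there is a safety concern, with infusion reactions as the example, "it is at the discretion of the investigator or his/her designee to adapt the infusion scheme". The listed options include "stopping the infusion, and provided no further safety concern exists, restarting at a slower rate". No RCTC grade is given and 4.2.2 is not mentioned.
- **4.2.2 (emergency procedures).** Depending on clinical course and medical judgment, "the infusion may be re-initiated in case of mild or moderate infusion reactions", with RCTC V2 as the grading scale and a lower starting speed that is raised gradually. For the most serious case it says "In case of suspected drug related anaphylactic reaction" that "the investigator should discontinue treatment permanently with BI 655130".
- **3.3.4.1 (discontinuation of trial treatment).** On restarting after a temporary stop, it cites 4.1.4 and 4.2.2 together, without ranking them.
- **5.2.4 (under other safety parameters).** After an infusion reaction, sites are to "grade the intensity of the reaction according to RCTC V2 grading (cf. ISF) and proceed as described in Section" 4.2.1. Section 4.2.1 deals with concomitant therapy, disease worsening and escape treatment; for example, "the choice of the escape treatment i.e Standard of Care treatment will be left at the discretion of the investigator". It has no text on infusion reactions.

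**The concern.** A restart rule is used at the bedside, under time pressure, by staff who may open only one section. Section 4.1.4 conditions restart on the absence of a remaining safety concern. Section 4.2.2 conditions it on the grade of the reaction. These are different tests, and neither section mentions the other.

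They can give different answers for a reaction that was severe, was not anaphylactic, and has settled. The protocol foresees severe infusion reactions: it addresses suspicion of them under adverse events of special interest in 5.2.5.1. Section 1.4 also commits to close monitoring because of a possible reaction in an earlier trial.

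The wrong reference in 5.2.4 adds to this. A site that grades the reaction and then follows the pointer arrives at text that does not help.

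What is at stake is consistent handling of the same event across sites, in the first trial of this antibody in atopic dermatitis.

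**Working it through.** No formula applies, because the point depends on no rate, sample size or test. The check is a comparison of the sections by type of reaction, using the intensity grades in 5.2.5.1 (mild, moderate, severe, life-threatening).

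| Reaction | 4.1.4 | 4.2.2 | Same answer? |
|---|---|---|---|
| Mild or moderate | Restart possible, slower, if no safety concern remains | Restart possible, slower, on medical judgment | Yes |
| Severe or worse, not anaphylactic, resolved | Restart possible on the same condition; no grade stated | Not among the reactions named for re-initiation; no explicit prohibition | Open to two readings |
| Suspected drug-related anaphylaxis | Not mentioned | Permanent discontinuation | 4.2.2 is explicit; 4.1.4 is silent |

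On infusion time there is no conflict: both sections cap the total at 180 minutes.

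Next, does any text rank the two sections? Section 4.1.4 does not cite 4.2.2, and 4.2.2 does not cite 4.1.4. Section 3.3.4.1 cites both for restart after a temporary stop and gives no order. It also points to 4.2 as a whole for stopping rules tied to specific adverse events. That favours 4.2.2 for stopping, but does not say which section decides on restart.

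Then the cross-references:

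- 5.2.4 points to 4.2.1, which has no infusion-reaction procedure.
- 6.2.2.1 says "Hypersensitivity reactions should be treated according to medical standards (See Section" 4.2.2), which is where the procedure stands.

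Two sections therefore send the reader to different places for the same kind of event, and only 6.2.2.1 sends them to the procedure.

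For context on frequency, section 1.2.3 describes at most two infusion reactions. One was in the multiple-dose volunteer trial at 20 mg/kg. The other was a feeling of heat in one patient, reported after the palmoplantar pustulosis results, with stable vital signs and recovery without treatment; the treatment arm is not given. The exposed total is 187 volunteers + 7 patients with generalised pustular psoriasis + 38 active-arm patients with palmoplantar pustulosis (19 + 19) = 232. Two in 232 is about 0.9%, for any grade. Neither event is described as severe. The total mixes doses, routes and populations, so it is background only and not a rate for this trial.

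**The case against.** The strongest reply is that there is no direct contradiction. Section 4.1.4 is a general paragraph on administration, and its discretion is conditional. Section 4.2.2 is specific to infusion reactions and adds a severity limit. A site must follow every section, so the two apply together and the more specific one controls. Both require a slower restart and the same time cap.

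Much of this stands. A reader might infer that 4.1.4 permits restart whatever the severity, but that takes silence for a rule and overlooks the condition that no safety concern remains. A reader might also infer that two sites could act in opposite ways and both comply. That is doubtful: if 4.2.2 is read as excluding severe reactions, a site that restarts after one departs from it. What does not stand is the claim that the text settles the matter. Section 4.2.2 is permissive and excludes severe reactions only by implication, and no passage gives it precedence.

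Later infusions are partly covered. Section 3.3.4.1 ends treatment when medical reasons, including adverse events, rule it out. Section 5.2.2 lets the investigator and the sponsor's trial manager agree on pre-medication. Neither is tied to severity, but the documents do not support a claim that later dosing is unaddressed.

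The site file may also say more, since 4.2.2 refers to its handling instructions for how an infusion is re-initiated. It is not available here.

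On the reference in 5.2.4, one can say that the heading of 4.2.1 mentions emergency procedures and that 4.2.2 follows directly. That makes the error easy to recover from, but it is still an error.

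**Conclusion.** The point holds as a minor inconsistency in safety conduct. The restart condition is stated differently in 4.1.4 and 4.2.2, no precedence is given, and a resolved severe non-anaphylactic reaction can be read two ways. The reference in 5.2.4 is wrong, and that part needs no interpretation.

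Two larger consequences might be inferred and are not supported. The first is a likelihood that such a reaction occurs among the roughly 45 patients. The documents give no rate of severe infusion reactions, so any such probability would rest on an invented input. The second is an effect on EASI50 or EASI75 at Week 16. The non-response rule in SAP 6.6.2 covers binary endpoints and applies after premature discontinuation of study medication, to data beyond the last dose plus four weeks. A changed result would need a severe reaction before Week 16, a discontinuation that turned on this wording, and a patient who would otherwise have responded. The primary mixed-model analysis of percentage change in EASI does not use that rule, and SAP 6.1 keeps the available data of patients who stop treatment but continue visits.

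The conclusion rests on the current protocol text and assumes that the unseen site file does not already resolve the question.

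**What to change.** The sponsor should:

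1. reconcile 4.1.4 with 4.2.2 so that one statement governs restart of an interrupted infusion, and make explicit how it applies to severe, non-anaphylactic reactions;
2. have 4.1.4 refer to that statement instead of giving its own condition;
3. change the cross-reference in 5.2.4 from 4.2.1 to 4.2.2;
4. check that the handling instructions in the site file agree with the reconciled text.

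Which clinical rule applies is the sponsor's decision, and no view is taken on it here. The cost is a protocol clarification and a note to sites. Assessments, sample size and analyses stay as they are.
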